8.1.4.6 Assessment of Plexa S DX lead handling (if applicable)

During implantation, the handling of the Plexa S DX lead will be assessed by the implanting physician. The following characteristics have to be assessed:

- How do you rate the flexibility of the Plexa ProMRI S DX ?
- How do you rate the push-ability of the Plexa ProMRI S DX?
- How do you rate the positioning behavior of the Plexa ProMRI S DX in the RV?
- How do you rate the extension/retraction behavior of the Plexa ProMRI S DX screw?
- How do you rate the X-ray visibility of the extended screw of the Plexa ProMRI S DX?
- How do you rate the fixation behavior of the Plexa ProMRI S DX?
- How do you rate the X-ray visibility of the Plexa ProMRI S DX in its final position?
- How do you rate the stylet handling in regard to the Plexa ProMRI S DX?

Ratings will be scored in the categories "Very good/good/adequate/poor/very poor".

The eCRF may be accepted as source document for the Plexa handling assessment. However, the use of a site-specific source data sheet is recommended.

8.1.4.7 Assessment of Selectra catheter handling (if applicable)

If a Selectra catheter (outer or outer and inner) is used to position the left ventricular lead, the implanting investigator will be asked to assess its features with regard to the following characteristics:

- Torqueability
- Flexibility (distal end)
- Gliding properties
- Lead delivery
- Slitability (i.e. the ease of slitting of the Selectra catheter)
- x-ray visibility
- Overall handling

Furthermore the investigator will be asked to assess the features of the Selectra Slitter Tool:

- Lead fixation mechanism
- Handling and design
- Slitting performance
- Overall handling

These ratings will be scored in the categories "Very good/good/adequate/poor/very poor". In addition, information about the use of further accessories will be collected.

The eCRF may be accepted as source document for the Selectra handling assessment. However, the use of a site-specific source data sheet is recommended.

8.1.4.8 Automatic LV VectorOpt test

The Automatic LV VectorOpt test has to be mandatorily performed in CRT-D patients. It is recommended to perform the test at pre-hospital discharge, but testing at implantation or at 3-month follow-up (if not done before) is also acceptable.

It is recommended to perform the measurement of RV/LV conduction times at the beginning of the test to facilitate the selection of vectors that are to be measured. In order to allow for a comparison of manual and automatic testing, the investigator is asked to perform the manual LV VectorOpt test first, the choice of at least 3 vectors being at the investigator's discretion. After that the automatic LV VectorOpt test shall be performed for the same subset of vectors. Finally, the automatic LV VectorOpt test will be performed for all 20 available vectors. Alternatively, a different subset of vectors at the investigator's discretion may be chosen for the automatic LV VectorOpt test.

Finally, the PNS thresholds shall be measured manually for a selection of vectors at the investigator's discretion.

The documentation in the eCRF will comprise of the following items:

- Did you perform the RV-LV conduction time test (RVp-LVs, RVs-LVs or both)? [Yes/No]
- Time needed to run the LV threshold measurement manually (and indication of the number of vectors tested)
- Time needed to run the Auto LV threshold measurement of the same subset of vectors (that were selected for the manual test)
- Time needed to run Auto LV threshold measurement (using all 20 vectors or for the selected vectors)
- Listing of pacing vectors that were tested during the automatic and/or manual procedure [Multiple choice]
- Number of vectors for which the PNS threshold was measured

- Values for sensing amplitude, pacing impedance, pacing threshold and PNS threshold of the finally programmed pacing vector
- Assessment of the Auto LV VectorOpt test by the investigator:
 - Do you consider the RV-LV conduction time test helpful? [Yes/No/Not done]
 - How did you preselect the pacing vectors that were measured automatically?
 - Intuitiveness of the threshold test (Score: "Very intuitive/intuitive/adequate/poor/very poor")
 - Ease to find the best LV pacing configuration (Score: "Very easy/easy/adequate/difficult/very difficult")
 - Did you program the permanent pacing vector directly from the result table of the Auto LVVO? [Yes/No]
 - Overall handling assessment of Auto LV VectorOpt feature (Score: "Very good/good/adequate/poor/very poor")
 - To what extent do you agree to the following statement relating to programmer-based LV vector optimization ("Strongly agree/Somewhat agree/Neither agree nor disagree/Somewhat disagree/Strongly disagree"):
 - "The parameters RV-LV conduction time, PNS threshold and impact on device longevity (pacing threshold) provide a good decision basis and are sufficient for a clinically acceptable LV vector optimization."
 - "Auto LV VectorOpt is an ergonomic tool for informed decision making and recommending which vector to select."
 - "The automatic measurement process simplifies the process of finding a suitable LV pacing vector for CRT."

The eCRF may be accepted as source document for the LV VectorOpt test assessment. However, the use of a site-specific source data sheet is recommended.

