1. A Kaplan-Meier estimate for the SADE-free rate at 3 and 12 months will be performed as a sensitivity analysis for the primary endpoint.
2. The Automatic LV VectorOpt test will be evaluated with regard to time savings, usability and acceptance criteria. This test was chosen as endpoint because it is a new feature that consists in a further development of the already known manual LV VectorOpt test which was investigated in the BIO|MASTER.Edora Family study.
3. The CRT AutoAdapt feature will be evaluated with regard to its programming, the behavior of the algorithm, usability and acceptance criteria. While CRT AutoAdapt aims at improving hemodynamics, it is not expected that significant effects on hemodynamics can be detected due to the small sample size and relatively short duration of this investigation. However, data on the functionality and acceptance of the feature contribute to this secondary endpoint that was chosen in order to gain more insight in the clinical use of this new feature.

¹ MEDDEV 2.7/1 Rev. 4

² MEDDEV.2.12/2 rev.2: 2012 Guidelines on Post Market Clinical Follow-up

BIOTRONIK SE & Co.KG // BIO|MASTER.Cor Family

Automatic LV VectorOpt and CRT AutoAdapt are new features that were implemented for the first time in BIOTRONIK devices and therefore chosen as secondary endpoints.

Another focus of the study is the data collection for the Plexa S DX lead with DF4 connection. For this reason data of interest are recorded to assess the atrial sensing performance and lead related adverse events but also the handling assessment during the implantation.

The product design of the DF4 variant of Plexa S DX is identical to the Plexa S DX DF-1 lead, except for the connector. In the BIO|MASTER.Ilivia Family/Plexa study, 27 Plexa S DX DF-1 leads were analyzed and already provided enough clinical data for the safety and efficacy of the DX lead variants²⁸. Therefore, 30 Plexa S DX leads with DF4 connection are considered to be sufficient for the evaluation in this study.

The decision to include the Plexa S DX lead into the Master Study for the Cor Family devices is based on the fact that Acticor/Rivacor VR-T DX is the only device on the market that is compatible with this new DX lead with DF4 connection. Thus, the requirements for a PMCF for both devices were combined in one study.

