7.2.2.2 Secondary endpoint 2: Automatic LV VectorOpt test (CRT only)

At pre-hospital discharge or at the latest at 3-month follow-up, the following endpoints related to the automatic LV VectorOpt test will be assessed:

- a. time needed to perform the LV threshold measurement manually
- b. time needed to perform the LV threshold measurement automatically
- c. investigator appraisal (score) of RV-LV conduction time test
- d. investigator appraisal (score) of intuitiveness of the threshold test
- e. investigator appraisal (score) of ease to find the best LV pacing configuration
- f. investigator appraisal (score) of overall handling of the Auto LV VectorOpt feature
- g. investigator agreement (score) to different statements relating to programmer-based LV vector optimization

Furthermore, the choice of tested vectors, the number of performed PNS threshold measurements, the finally programmed settings and details on the use of the test page will be recorded as further data of interest (see 7.5.2).

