8.1.3 Selection of measurements for endpoints

For the primary endpoint, the SADE-free rate will be assessed by collecting and evaluating adverse events until the 3-month follow-up. This assessment was chosen to comply with preceding studies regarding result consistence and comparability and regarding acceptance by regulatory authorities outside Europe. As one objective of secondary endpoint 1 is a sensitivity analysis for the primary endpoint, the assessment of data – collection and evaluation of adverse events within a pre-specified timeframe – must be consistent between these endpoints. Secondary endpoint 2 aims at evaluating the Automatic LV VectorOpt test feature. The measurements were selected in order to collect data to support the intended claims for this feature (see section 7.3). As the CRT AutoAdapt feature (secondary endpoint 3) will be turned on at pre-hospital discharge (if applicable), its acceptance and performance is assessable through the measurement of device parameters – such as reprogramming, percentage CRT pacing etc. – at subsequent follow-ups. The percentage of CRT pacing is a crucial parameter for the effectiveness of cardiac resynchronization therapy. Evaluation of the CRT AutoAdapt performance using CRT response parameters is not feasible due to the small sample size of this study.

For both endpoints, Auto LV VectorOpt and CRT AutoAdapt, usability, user acceptance, clinical acceptability and overall assessments by the investigator play an important role, also with respect to validation of claims. However, these characteristics are very subjective, hardly measurable through device parameters, and hence commonly assessed by questionnaires. Therefore, scores with five categories (e.g. "Very good/good/adequate/poor/very poor") were chosen to rate these properties. Comment fields will be used to justify the chosen category.

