13.2 Variables

CIP chapter 7.2.2.2 Secondary endpoint 2: Automatic LV VectorOpt test (CRT only)

At Pre-Hospital Discharge or at the latest at 3-month follow-up, the following endpoints related to the automatic LV VectorOpt test will be assessed:

- a. time needed to perform the LV threshold measurement manually
- b. time needed to perform the LV threshold measurement automatically
- c. investigator appraisal (score) of RV-LV conduction time test
- d. investigator appraisal (score) of intuitiveness of the threshold test
- e. investigator appraisal (score) of ease to find the best LV pacing configuration
- f. investigator appraisal (score) of overall handling of the Auto LV VectorOpt feature
- g. investigator agreement (score) to different statements relating to programmer-based LV vector optimization

Data file identifier patient_display_id_full	Notes	Variable name	Variable label	Variable level	Nominal values
auto_lv_vectoropt	descriptive (a)	DULVTHMT	Time needed to run the LV threshold measurement manually	scale hh:mm:ss has to be converted to min	n.a.
	descriptive (b)*	DULVTHAT	Time needed to run the LV threshold measurement automatically (same subset of vectors)	scale hh:mm:ss has to be converted to min	n.a.

Data file identifier patient_display_id_full	Notes	Variable name	Variable label	Variable level	Nominal values
auto_lv_vectoropt	descriptive (c)	DURVLVAS	Do you consider the RV-LV conduction time test helpful?	nominal	 Yes  No  Not done
	descriptive (d)	DUITHTAS	Intuitiveness of the threshold test	nominal	 Very intuitive  Intuitiv  Adequate  Difficult  Very difficult
	descriptive (e)	DUBLVPAS	Ease to find the best LV pacing configuration	nominal	 Very easy  Easy  Adequate  Difficult  Very difficult
	descriptive (f)	DULVVOAS	Overall Handling assessment of the Auto LV VectorOpt feature	nominal	 Very good  Good  Adequate  Poor  Very poor

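### By protocol the manual LV threshold test comes before the automatic one, so any time difference between them for secondary endpoint 2 is confounded with test order

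*Protocol*

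**What the plan says.** Protocol section 5.3 gives the aim of secondary endpoint 2: "The Automatic LV VectorOpt test will be evaluated with regard to time savings, usability and acceptance criteria". Section 7.2.2.2 lists as its first two items the "time needed to perform the LV threshold measurement manually" and the corresponding automatic time. Section 8.1.3 explains the choice: "The measurements were selected in order to collect data to support the intended claims for this feature".

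Section 8.1.4.8 sets the procedure and states its purpose: "In order to allow for a comparison of manual and automatic testing". The sequence for this begins with the operator-run measurement: "the investigator is asked to perform the manual LV VectorOpt test first, the choice of at least 3 vectors being at the investigator's discretion". The step that follows is then given: "After that the automatic LV VectorOpt test shall be performed for the same subset of vectors". An automatic run on all vectors, or on another subset, comes after that, and phrenic nerve thresholds are measured last. Measuring RV/LV conduction times at the outset is recommended to help choose vectors.

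SAP section 13.2 summarises the manual and automatic times as two separate descriptive variables. Section 13.6 has no hypothesis for them, and section 5.3 treats everything except the primary endpoint as exploratory. SAP section 9.2.6 records whether both tests used the same subset.

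**The concern.** This is a two-period, within-patient comparison with a single sequence. The second test follows a first test on the same lead and vectors, with the manual thresholds already known. The first may include work that is not repeated, such as opening the page or settling on vectors. Fatigue or interruption could instead slow the second. Whatever the net effect, it falls on the automatic test in every patient who follows the sequence.

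Nothing in the plan separates the two influences. Protocol section 8.1.2, on bias, deals with operating procedures, follow-up scheduling and the cap on patients per site, but not with test order. The eCRF list in 8.1.4.8 and the readable SAP tables have no field for order, no definition of when either clock starts, and no paired-difference variable.

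At stake is whether a time difference can be attributed to the automatic method. Two mean times reported side by side invite that reading even without a test.

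**Working it through.** The plan states no figure for this comparison. Its only sample size (114 evaluable, 127 enrolled) is for the primary endpoint and uses none of these times.

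**Patients exposed.** Protocol section 8.2.4 plans 15 HF-T and 52 HF-T QP devices: 15 + 52 = 67 CRT-D patients. If the roughly 10% loss in section 11.4 (stated for the primary analysis set) applied here too, 67 × 0.9 ≈ 60 would remain.

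**Fixed order.** Let τ be the true saving (manual minus automatic) and d the time by which a test is shortened because it comes second; d may be negative. With manual always first:

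E[manual − automatic] = τ + d.

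Only the sum can be estimated, whatever n is.

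**Both orders, equal numbers.**
- Additive effect, the same in both sequences: [(τ + d) + (τ − d)] / 2 = τ.
- Unequal effects, where manual-first adds d1 and automatic-first subtracts d2: [(τ + d1) + (τ − d2)] / 2 = τ + (d1 − d2)/2. A remainder is left unless d1 = d2.

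**Illustration (all times assumed).** Take manual 6 min and automatic 4 min, so τ = 2.0, and let the second test take a fraction (1 − g) of its usual time. Fixed order gives 6 − 4(1 − g) = 2 + 4g. Balanced order gives the mean of 6 − 4(1 − g) and 6(1 − g) − 4, which is 2 − g.

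| g | fixed order (min) | balanced (min) |
|---|---|---|
| −0.2 | 1.2 | 2.2 |
| −0.1 | 1.6 | 2.1 |
| 0 | 2.0 | 2.0 |
| 0.1 | 2.4 | 1.9 |
| 0.2 | 2.8 | 1.8 |
| 0.3 | 3.2 | 1.7 |

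A proportional effect is not removed entirely by balancing, but the remainder is a quarter of the fixed-order bias here. With no true saving (6 and 6 min), fixed order gives 6g, a false saving of 0.6 to 1.8 min for g of 0.1 to 0.3; balanced order gives 0.

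**In units of the SD of the paired differences.** With no true saving, the chance that the whole 95% CI lies above zero under fixed order is:

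| order effect | n = 67 | n = 60 |
|---|---|---|
| 0 | 0.025 | 0.025 |
| 0.2 SD | 0.36 | 0.33 |
| 0.3 SD | 0.68 | 0.63 |

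The chance rises with n, so a larger sample makes a spurious difference more convincing.

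**Precision.** The 95% CI half-width for a mean paired difference is t(0.975, n − 1)/√n: 0.24 SD at n = 67 and 0.26 SD at n = 60. Splitting 67 patients 34/33 between orders gives a standard error of ½√(1/34 + 1/33) = 0.122 SD, equal to 1/√67 = 0.122, if the within-order SD is the same. Alternation costs essentially no precision.

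**The case against.** The strongest reply is that the bias may be negligible or run against the device. The recorded quantity is labelled "Time needed to run the LV threshold measurement manually", which need not include set-up or vector choice, and the recommended conduction-time test already helps with that choice. The automatic test measures preselected polarities by itself (protocol section 4.7.1.2), so it may depend little on operator practice, and nothing in the documents suggests that it runs faster once manual thresholds are known. Phrenic nerve thresholds are measured separately afterwards. The times are descriptive, and the contents of the promotional claims table in section 7.3 are not readable, so the wording of any time claim is unknown.

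This stands as far as direction, size and weight are concerned. A reader might infer that the saving is likely inflated in the device's favour. The documents do not support that: they give no order effect of either sign, and the undefined clock leaves open whether set-up is counted. A reader might also infer that alternation would bring the bias to zero. That holds only for a symmetric additive effect. Manual testing is operator-driven, so known automatic thresholds could shorten a later manual test more than the reverse, and balancing would then understate the saving. Finally, the investigator is asked, not compelled, to test manually first, so the order holds by protocol rather than without exception.

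None of this separates method from order. The same-subset question in the SAP captures differences in vectors, not in sequence.

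**Conclusion.** The confounding follows from the text alone: by protocol, any manual-minus-automatic difference for secondary endpoint 2 mixes method with order, in up to 67 patients. Inflation is possible, but neither its direction nor its size can be established. The minute and SD figures above rest on assumed times and order effects and show sensitivity only. The weight is modest, because the endpoint has no hypothesis and all non-primary analyses are exploratory. The primary endpoint, its power and its sample size are untouched. The point is still worth acting on, because time savings is a stated evaluation aim, the data are meant to support claims for the feature, and the correction is cheap.

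**What to change.** In protocol section 8.1.4.8:
- have the investigator choose the subset of at least 3 vectors before either test;
- start each clock at the first threshold measurement;
- alternate the order by patient ID (for example odd numbers manual first, even numbers automatic first);
- record the actual order on the eCRF;
- leave the all-vector automatic run and the phrenic nerve measurements last.

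In SAP section 13, report the within-patient paired difference with a 95% CI, averaged over the two orders and also shown separately by order. Include the comparison restricted to each patient's first test (manual times in manual-first patients against automatic times in automatic-first patients). It is a between-patient comparison and less precise, but it is free of carry-over.

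The cost is a CIP amendment, one eCRF field, site instruction and a short SAP addition, with no extra patients or tests. Protocol section 13 classes changes to procedures or analysis as substantial, so ethics approval must come first. Some sites may follow the wrong order, which the new field would show. Carry-over may be asymmetric, so balancing need not remove all bias; the by-order display makes any remainder visible.

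If the order can no longer be changed, report the paired difference, state the confounding, and do not attribute the difference to the automatic method alone.

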8.1.4.9 CRT AutoAdapt (only Acticor 7 and Rivacor 7 CRT-Ds)

At implantation and/or pre-hospital discharge CRT AutoAdapt shall mandatorily be programmed 'ON' in all CRT-D patients that are implanted with Acticor 7 or Rivacor 7, with the exception of patients with AV block, for whom this feature is contraindicated. (Note: CRT AutoAdapt is not available in Rivacor 5.) The feature may be programmed 'OFF' in exceptional cases without causing a deviation from this clinical investigator plan, provided that the investigator gives a sound reasoning for his decision, e.g. special medical condition of the patient.

At 3-month follow-up the following data will be recorded:

- Was the feature programmed 'ON'?
- If "no", why not?
- Programmed setting for ventricular pacing and programmed AV delays
- Mean percentage of CRT pacing since last follow-up
- Mean percentages of adaptive BiV pacing, programmed BiV pacing and adaptive LV pacing, respectively, since last follow-up
- Mean adapted AV delay after pace/sense
- Assessment of the feature by the investigator:
 - Programmability (Score: "Very easy/easy/adequate/difficult/very difficult")
 - Clinical acceptability of the algorithm's decisions (Score: "Very good/good/adequate/poor/very poor")
 - Overall assessment of the CRT AutoAdapt feature (Score: "Very good/good/adequate/poor/very poor")

The eCRF may be accepted as source document for the assessment of the CRT AutoAdapt feature. However, the use of a site-specific source data sheet is recommended.

- Is the programming of CRT AutoAdapt maintained at the end of the follow-up? If "no", why not?

At 3-month and subsequent follow-ups it is the investigator's decision to leave the feature activated or to deactivate it.

If the feature remained active until the 12-month follow-up, the investigator will again be asked for an overall assessment of CRT AutoAdapt.

In addition to the data collected during follow-up visits, Home Monitoring data may be analysed with regard to the behaviour of the algorithm, e.g. mean percentage of adaptive BiV pacing, programmed BiV pacing and adaptive LV pacing, respectively.

8.1.4.10 AV delay optimization (for VR-T DX, DR-T, and Rivacor 5 HF-T and HF-T QP devices)

For all patients with VR-T DX or DR-T devices (only if clinically indicated), and for patients with Rivacor 5 triple-chamber devices (as Rivacor 5 is not equipped with CRT AutoAdapt) with sinus rhythm of sufficient intrinsic rate, the AV Opt test has to be performed during the PHD follow-up³. Performance of the test during the 3-month follow-up is acceptable if it was not done at PHD.

It is the decision of the investigator whether to perform additional AV delay optimization procedures, e.g. Echo, or not.

The eCRF will comprise questions about measured data as well as the assessment of the test procedure(s):

- Did you run the AV Opt test? [yes/no]
 - If not, why?: [Multiple choice - Select all that apply]
 - General lack of trust in automated test routines
 - Personal or institutional preference for use of alternative methods
 - Patient conditions prescribe AV delay settings without need for additional diagnostic aids
 - Atrial fibrillation
 - No sufficient intrinsic rate
 - Other [please describe]
 - If yes: Did the test suggest sensed and paced AV delay values? [yes/no]
- Please give the values for the final, programmed AV delay settings (after pace):
 - AV delay @ 60 bpm: [value]
 - AV delay @ 80 bpm: [value]
 - AV delay @ 100 bpm: [value]
 - AV delay @ 120 bpm: [value]
 - AV delay @ 140 bpm: [value]
- Please provide the clinical basis for the final, programmed AV delay settings [yes/no; Select all that apply]
 - Based upon the AV Opt test output
 - Based upon the use of a personal/institutional preference
 - Based upon data from other follow-up affiliated diagnostics
 - Adoption of values from the device's standard program

³ If the implantation and PHD are not on one or two consecutive days, the measurements can be done between implantation and patient discharge.

- Retention of AV delay settings from interrogated program
- Long AV delay to avoid ventricular pacing
- Other reason [please describe]
- If programmed setting is *not* based on AV Opt test output, or if a long AV delay was programmed to avoid ventricular pacing: Do you consider the suggested AV delay clinically acceptable? [yes/no; Reason]
- Overall assessment of the AV Opt tool (Score: "Very good/good/adequate/poor/very poor")

The eCRF may be accepted as source document for the assessment of the AV Opt feature. However, the use of a site-specific source data sheet is recommended.

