4.7.1.3 CRT AutoAdapt (CRT only)

The hemodynamic benefit of CRT depends on the setting of an AV-delay that allows the full atrial contribution for optimal filling of the ventricles and the setting of a ventricular pacing configuration that ensures ventricular synchronization for optimal ejection. Observational studies have identified suboptimal programming of the AV and VV delays as determinant factor of a poor response to CRT²⁵. Since physiologic conditions change over the day and also on a longer scale with cardiac remodeling, the settings need frequent adaptation to ensure optimal benefit of CRT. Therefore, the adaptive CRT AutoAdapt algorithm (see Figure 5) can be used to adjust the AV-delay and set the ventricular pacing configuration to BiV or LV, based on periodic automatic measurement of electrical intra-cardiac conduction times (see Table 3). (*Ventricular pacing configuration 'LV' is sometimes called 'LV only' pacing configuration.*)

The pre-conditions for CRT AutoAdapt activation or continuation are an atrial heart rate below 100 bpm and an AV conduction time after pace of less than 250 ms. Switching to *LV only pacing* is only allowed if LV Capture Control is enabled. This is to ensure that the LV only mode cannot be activated if the LV pacing threshold is not sufficient.

If the measurements of conduction times indicate that the condition for starting/continuing CRT AutoAdapt are not fulfilled (see Figure 5), the algorithm switches back to the BiV pacing settings that the physician programmed before activating CRT AutoAdapt.

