Regarding the CRT AutoAdapt feature, the available clinical data show beneficial effects of continuous automatic, ambulatory CRT optimization over standard echo-guided optimization at implant. Ambulatory CRT optimization was associated with a higher proportion of patients receiving effective CRT, an improved Clinical Composite Score (CCS), a reduction in HF hospitalization, the reduced occurrence of AF and death. Since AdaptivCRT (aCRT, a competitive algorithm) and the functionally similar CRT AutoAdapt require intact AV node, right bundle conduction, and absence of atrial tachycardia, patients fulfilling these criteria were shown to benefit more than the overall collective patients with CRT indication. Furthermore, LV-only pacing, i.e. withholding right ventricular pacing when intrinsic electrical conduction to the right ventricle is normal, was shown to result in similar or superior LV function and was also associated with improved RV function vs. BiV pacing⁴³⁻⁴⁶. It was criticized that the entirety of findings regarding clinical outcomes of aCRT is based on only one prospective trial and associated retrospective subgroup analyses. However, based on available data, aCRT and most probably also CRT AutoAdapt offer clinicians and patients enhanced options to improve response to CRT.

The use of Home Monitoring functionality offers the physicians the possibility to monitor their patients remotely whenever it is deemed necessary. The automatic early detection of arrhythmia and device anomalies allows earlier medical intervention as compared to conventional in-office follow-ups. The results of the TRUST clinical study demonstrated the safety and effectiveness of the remote monitoring⁴⁷. In the Cor Family ICDs, the QuickCheck feature offers the additional advantage of providing a "real-time" report including a current periodic IEGM typically within 3-4 minutes of triggering it, e.g. if the patient experiences symptoms.

Finally, the new design of the Cor Family devices is expected to provide greater patient comfort and a better cosmetic outcome.

The individual benefit of study participation for the patient is an intensified medical supervision of his clinical status. In CRT-D patients the chance of responding to CRT-D therapy might be increased due to the increased number of LV pacing vectors, MultiPole Pacing and CRT AutoAdapt.

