cardiac_diagnostic	descriptive	EGHRT	Heart rate [bpm]	scale	n.a.
	descriptive	CVEGARH	Atrial rhythm during ECG recording	nominal	
  Sinus rhythm  Atrial fibrillation  Atrial flutter/other SVT  Atrial paced rhythm  Other
	descriptive	CVEGVRH	Ventricular rhythm during ECG	nominal	
  Intrinsic – atrial conducted  Intrinsic – escape rhythm  Ventricular paced rhythm  Other
	descriptive for CVEGVRH ≠ ventricular paced rhythm	EGPRI	PR interval [ms]	scale	n.a.
	descriptive	EGQRS	QRS width (intrinsic) [ms]	scale	n.a.
	descriptive	EGQRSM	QRS morphology	nominal	
  Normal  LBBB  RBBB  Indeterminate

Data file, identifier patient_display_id_full	Notes	Variable name	Variable label	Variable level	Nominal values
cardiac_diagnostic	case listings for CVEGARH = Other	COEGARH	Specification of other atrial rhythm during ECG recording	text	n.a.
	case listings for CVEGVRH = Other	COEGVRH	Specification of other ventricular rhythm during ECG recording	text	n.a.

Cardiac diagnostic / LVEF

Data file, identifier patient_display_id_full	Notes	Variable name	Variable label	Variable level	Nominal values
cardiac_diagnostic	descr.	EHLVEF	Left ventricular ejection fraction [%]	scale	n.a.

Cardiac diagnostic / therapy indication

Data file, identifier patient_display_id_full	Notes	Variable name	Variable label	Variable level	Nominal values
cardiac_diagnostic	descr.	CECRT	CRT indication given	nominal	 Yes  No
	descr.	CECRTTYP	Type of CRT indication	nominal	 CRT indication in sinus rhythm  CRT indication in atrial fibrillation  CRT indication and conventional pacing indication  Other
	descr.	CEICDIND	ICD indication given	nominal	 Yes  No

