14.1 Analysis set

All analyses are performed for the CRT AutoAdapt analysis set.¹¹⁰

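### Secondary endpoint 3 pools CRT-D patients in continuous AF, or with AutoAdapt left OFF, with those in whom the algorithm can run, so its adaptive pacing figures are hard to read

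*Protocol*

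**What the plan says.** **Who is to have the feature ON.** Protocol 8.1.4.9 covers all CRT-D patients with Acticor 7 or Rivacor 7, "with the exception of patients with AV block, for whom this feature is contraindicated". Sections 9.3 and 9.4 word the exception more narrowly, as chronic complete AV block. Section 8.1.4.9 adds: "The feature may be programmed 'OFF' in exceptional cases without causing a deviation from this clinical investigator plan", provided the investigator gives a sound reason.

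**When it can run.** Protocol 4.7.1.3: "The pre-conditions for CRT AutoAdapt activation or continuation are an atrial heart rate below 100 bpm", together with an upper limit on AV conduction time. If the conditions fail, "the algorithm switches back to the BiV pacing settings that the physician programmed before activating CRT AutoAdapt". Protocol 6.1 says this algorithm and a similar competitor "require intact AV node, right bundle conduction, and absence of atrial tachycardia".

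**Who is enrolled.** Permanent atrial tachyarrhythmia is an exclusion for VR-T DX devices only (8.3.3). SAP 8.2.1 lists "CRT indication in atrial fibrillation" as a type of CRT indication and permanent as a type of AF.

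**What is analysed.** SAP 14.1: "All analyses are performed for the CRT AutoAdapt analysis set". The visible variable label in SAP 7.5 defines that set by Acticor 7 or Rivacor 7 HF model and implantation attempt. Items 3b to 3d come from Home Monitoring (SAP 14.2), with no visible condition on rhythm or on the feature being ON. SAP 5.6 plans no analyses repeated in subsets, and SAP 5.4 plans no imputation.

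**The concern.** Protocol 5.3 says endpoint 3 is to evaluate, among other things, how the algorithm behaves. While a patient is in AF the pre-condition is not met, so that time is expected to count as programmed BiV pacing rather than adaptive pacing. It says little about what the algorithm does when it is able to run. Pooling such patients with the rest gives one adaptive percentage that depends on both the algorithm and the rhythm mix of the sample. A low figure could be taken for poor uptake of adaptation, and a wide spread for erratic behaviour.

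The protocol does allow for rhythm in the sister feature. In 8.1.4.10 the Rivacor 5 CRT-D patients are those "with sinus rhythm of sufficient intrinsic rate, the AV Opt test has to be performed", and AF is a listed reason for not running that test. For AutoAdapt, the 3-month deactivation item in SAP 14.2 offers only chronic complete AV block or other.

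**Working it through.** **The plan's own figures.** Endpoint 3 has no stated sample size, effect or hypothesis, so there is nothing of its own to reproduce. The primary sample size does reproduce and is not affected. An exact binomial test of 90% against 98%, with 2.5% in the upper tail, gives N = 114 (at least 109 SADE-free, alpha 0.0239, power 0.9725), and 114 / 0.90 = 126.7, rounded up to 127.

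**Inputs for the illustration**
- Planned CRT-Ds (Protocol 8.2.4): 15 HF-T + 52 HF-T QP = 67. This is an upper bound for the AutoAdapt set, because Rivacor 5 models lack the feature.
- f, the share of the set with AF: not in the documents; assumed 10% to 25%.
- t, the fraction of the interval those patients spend in AF: 1 if continuous, 0.5 as an example of intermittent AF.
- m, mean adaptive pacing in patients who meet the pre-condition: not in the documents; assumed 60%, with 80% as a check.
- The device is assumed to treat AF as an atrial rate of 100 bpm or more and to store 0% adaptive pacing for that time. The documents state neither.

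**Number of patients.** 67 × 0.10 = 6.7 and 67 × 0.25 = 16.8, so about 7 to 17 at most.

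**Pooled mean.** Observed mean = m × (1 − f × t).

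| m | f | t = 1 | t = 0.5 |
|---|---|---|---|
| 60% | 10% | 60 × 0.90 = 54.0% | 60 × 0.95 = 57.0% |
| 60% | 25% | 60 × 0.75 = 45.0% | 60 × 0.875 = 52.5% |
| 80% | 3 of 67 | 80 × 64/67 = 76.4% | 78.2% |
| 80% | 20 of 67 | 80 × 47/67 = 56.1% | 68.1% |

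**Items one by one.** For 3b and 3d, time in AF lowers the adaptive percentages. For 3c, the same time is added to programmed BiV. For 3e, the mean is not pulled towards zero. A patient with no adapted AV delay drops out because nothing is imputed, so 3e describes only patients in whom the algorithm ran.

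**Patients left OFF.** The visible set label does not remove them. They either contribute no adaptive pacing or have missing values, and the visible text does not say which.

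**The case against.** A reader might infer more than the documents support, in five ways.

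- **That AF patients must be ON, so restricting to ON patients would change nothing.** The OFF clause in 8.1.4.9 lets an investigator leave the feature off with a sound reason and no deviation. How many AF patients would be ON is unknown. The clause does not settle the matter, because it is discretionary, does not mention AF, and leaves OFF patients in the set.
- **That any AF gives zero adaptive pacing and no adapted AV delay.** This fits only AF lasting the whole interval. Intermittent AF has a partial effect, and the stored 0% is itself an inference.
- **That 3e hides its smaller denominator.** The standard table for scale data in SAP 5.1.3 prints the non-missing N, so the count can be read off.
- **That a low adaptive figure could not be traced to AF at all.** AF type, CRT indication and ECG rhythm are tabulated at baseline (SAP 8.2.1), RA rhythm at every visit (SAP 8.2.4), and 3c shows the share of programmed BiV. Medians and quartiles are also planned. None of these is visibly crossed with 3b to 3e.
- **That the SAP certainly has no restriction.** The text of the footnotes to SAP 7.5, 14.1 and 14.2 is not visible, so a condition there cannot be ruled out.

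It can also be argued that reverting at a high atrial rate is part of the algorithm's behaviour, and that Protocol 5.3 wants insight into clinical use of the feature. That supports keeping the all-patient figures. It does not argue against showing the split beside them.

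**Conclusion.** The point holds as a minor one. In the visible text, endpoint 3 pools patients in whom the algorithm can run with patients in continuous AF and patients left OFF, and no planned table separates them. The direction for 3b, 3c and 3d follows from Protocol 4.7.1.3, given the assumption on how AF is sensed and stored. The size is not known. The illustrated loss of 6 to 15 points on a 60% mean rests wholly on the assumed AF share and adaptive percentage, and is half that if AF is present half the time. The endpoint is descriptive (SAP 14.6), so no hypothesis, error rate or primary result is touched. A restriction in the unseen footnotes would narrow or remove the point.

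**What to change.** In SAP 14.2 keep the all-patient figures and add rows for 3b to 3e in patients with AutoAdapt ON during the interval measured. Split these rows by permanent or long-standing persistent AF versus neither, and read algorithm behaviour from the rows without such AF. Use CVAFBTYP and CECRTTYP for the split, supported by the per-visit RA rhythm DURAMRH, because the baseline ECG may be missing or up to 3 months old. Take ON status from the AutoAdapt variables already in SAP 14.2. Add a sentence in SAP 5.6 noting these descriptive rows.

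Separately, the sponsor should reconcile the mandatory-ON passages (8.1.4.9, which says AV block; 9.3 and 9.4, which say chronic complete AV block) with each other and with 4.7.1.3 and 6.1. No clinical rule is proposed here.

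The cost is SAP wording and a few table rows, with no new data collection. The downside is smaller groups per row.
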